#### Table 5: Summary of dimensions and clusters of items of the IDEEL questionnaire

| Module                            | Dimensions                                | Number of
items | Cluster of
items | Direction of dimension scores                                    |
|-----------------------------------|---|--------------------|---------------------|--|
|                                   | Impact on Daily Activities                | 6                  | 1-6                 | Higher score = less impact on daily activities                   |
| Dry Eye Impact on
Daily Life   | Emotional Impact due to Dry Eye           | 11                 | 10-20               | Higher score = less emotional impact                             |
|                                   | Impact on Work due to Dry Eye             | 5                  | 23-27               | Higher score = less work impact                                  |
| Dry Eye Symptom-
Bother        | Dry Eye Symptom-Bother                    | 20                 | 1-20                | Higher score = greater symptom bother                            |
| Dry Eye Treatment
Satisfaction | Satisfaction with Treatment Effectiveness | 4                  | 2-5                 | Higher score = greater satisfaction with treatment effectiveness |
|                                   | Treatment- Related Bother / Inconvenience | 4                  | 6, 8-10             | Higher score = less treatment related bother                     |

# 12.4 Corneal and Conjunctiva Vital Staining with Fluorescein (NEI scale)

Corneal staining total score is defined as the sum of scores from 5 corneal areas: Central, Superior, Temporal, Nasal, and Inferior. The score for each area ranges from 0 to 3. Thus, the corneal staining total score can range from 0 to 15.

The conjunctiva is divided into a superior paralimbal area, an inferior paralimbal area and a peripheral area with a grading scale of 0-3 and with a maximal score of 9 for the nasal and temporal conjunctiva. Thus, the conjunctival staining total score can range from 0 to 18.

Corneal and conjunctiva vital staining total score is the sum of corneal staining total score and conjunctiva total score.

Information from blinded reading center and site investigators will be used as described in section 7.8.

#### 12.5 Partial date conventions

| AE START DATE   | AE STOI           | P DATE     | RULE for TEAE definition  | RULE for "Treatment"/"Follow-up" study period
definition for TEAE summaries   |
|---|-------------------|------------|---|---|
| Known   | Known,
Missing | Partial or | If AE start date < IMP start date, then not TEAE
If AE start date >= IMP start date, then TEAE | 
 
In case of Treatment Discontinuation:
 
If start date > Date of last IMP intake, then Follow-up study period for TEAE occurrence.
 
Otherwise, Treatment study period for TEAE occurrence.
 
In case of NO Treatment Discontinuation:
 
If start date ≥ Date of "Day 21" visit, then Follow-up study period for TEAE occurrence.
 
Otherwise, Treatment study period for TEAE occurrence.
 
 |
| Partial, but known components show
that it cannot be on or after IMP start
date | Known,
Missing | Partial or | Not TEAE  | Not applicable  |
|   |                   |            |   |   |

 Table 6: Algorithm for Treatment Emergence of Adverse Events

| AE START DATE                                | AE STOP DATE | RULE for TEAE definition   | RULE for "Treatment"/"Follow-up" study period definition for TEAE summaries |
|--|--------------|--|---|
| Partial, could be on or after IMP start date | Known        | If AE stop date < IMP start date, then not TEAE  | If TEAE, then Treatment study period for TEAE                               |
|  |              | If AE stop date $\geq$ IMP start date, then TEAE   |   |
|  | Partial      | Impute stop date as latest possible date (i.e. last day of month if day unknown or 31st December if day and month are unknown), then:    |   |
|  |              | If AE stop date < IMP start date, then not TEAE  |   |
|  |              | If AE stop date >= IMP start date, then TEAE   |   |
|  | Missing      | Assumed TEAE   |   |
|  |              |  |   |
| Missing                                      | Known        | If AE stop date < IMP start date, then not TEAE  | If TEAE, then Treatment study period for TEAE                               |
|  |              | If AE stop date >= IMP start date, then TEAE   | occurrence.   |
|  | Partial      | Impute AE stop date as latest possible date (i.e. last day of month if day unknown or 31st December if day and month are unknown), then: |   |
|  |              | If AE stop date < IMP start date, then not TEAE  |   |
|  |              | If AE stop date >= IMP start date, then TEAE   |   |
|  | Missing      | Assumed TEAE   |   |

NOTE: Assignment to "Treatment" or "Follow-up" study period is applicable only for TEAEs.

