## 8.3.2. Severity of AEs

The Investigator will grade the severity of any AE using the definitions in the Table below. For each episode, the highest severity grade attained should be reported.

Mild	Grade 1 - Does not interfere with patient's usual function (awareness of symptoms or signs, but easily tolerated [acceptable]).
Moderate	Grade 2 - Interferes to some extent with patient's usual function (enough discomfort to interfere with usual activity [disturbing]).
Severe	Grade 3 - Interferes significantly with patient's usual function (incapacity to work or to do usual activities [unacceptable])

[figure not shown]

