## 9.4.5. Analysis of safety variables

Adverse events (AEs) will be coded by System Organ Class (SOC) and Preferred Term (PT), using the Medical Dictionary for Regulatory Activities (MedDRA).

Treatment-emergent AEs (TEAEs) are all events occurring or worsening after the first dose of the IMP. TEAEs will be presented by treatment arm in terms of number of AEs and their incidence by System Organ Class

(SOC) and Preferred Terms (PT) using MedDRA. Analyses will be provided also by seriousness, relationship to treatment, severity and study period (treatment or follow-up).

Individual AEs will be listed in patient data listings.

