# 11. Evaluation of Safety

#### **11.1** Adverse events

Adverse Events (AEs) started before administration of study treatment will be considered as pretreatment; any AE started on or after the date of the first dose of study medication or started prior to first dose and worsened in severity after the first dose will be considered as Treatment-Emergent Adverse Event (TEAE).

In case of missing or incomplete dates not allowing a direct allocation to any of the two categories of AEs (pre-treatment/TEAE), an allocation will be done according to the available parts of the onset and the end dates (see Table 6). In case of TEAE, the event can be further classified as:

- On Treatment period, or
- On Follow-up period

according to the available parts of the onset and the end dates (see Table 6).

All AEs will be coded by SOC and PT according to MedDRA thesaurus. In addition, each AE will be graded to capture the relationship to IMP and severity (see protocol for details).

Pre-treatment AEs will be presented in the listings only.

TEAE summaries will be presented, displaying frequencies and percentages of patients reporting AEs within each SOC in decreasing order of total frequency. Along with AEs, number of events will be reported. On each of these summaries, patients will be counted only once per SOC and, withing each SOC, patients will be counted only once per PT.

"Possible", "Probable" and "Highly Probable" or missing relationships will be considered as related to study drug (ADR – Adverse Drug Reaction) for the summary tables. "None" and "unlikely" relationships will be considered not related to study drug.

The following table will be presented by treatment group and overall:

- A summary overview (patient with at least one event, percentage, and number of events) of:
  - o TEAEs,
  - Ophthalmic TEAEs,
  - Non-Ophthalmic TEAEs,
  - o severe TEAEs,
  - o severe Ophthalmic TEAEs,
  - o severe Non-Ophthalmic TEAEs,
  - o serious TEAEs,
  - o serious Ophthalmic TEAEs,
  - o serious Non-Ophthalmic TEAEs,
  - o non-serious TEAEs,
  - o ADRs,
  - Ophthalmic ADRs,
  - Non- Ophthalmic ADRs,
  - o serious ADRs,
  - TEAEs leading to discontinuation of IMP,
  - TEAEs leading to discontinuation of study,
  - TEAEs leading to death.

The following tables will be presented by treatment group:

- Summary of Ophthalmic TEAEs by primary SOC and PT and by study period (on treatment/follow-up and overall).

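### Two rows of SAP Table 6 class adverse events that start before dosing as not treatment-emergent even if they worsen on treatment, contradicting SAP 11.1 and Protocol 9.4.5

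*SAP*

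**What the plan says.** Protocol section 9.4.5 gives the definition: "Treatment-emergent AEs (TEAEs) are all events occurring or worsening after the first dose of the IMP". SAP section 11.1 repeats it in more detail. Besides events starting on or after the first-dose date, an event that "started prior to first dose and worsened in severity after the first dose will be considered as Treatment-Emergent Adverse Event" qualifies.

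SAP section 12.5, Table 6, sets out the algorithm. Its first row, for known start dates, reads "If AE start date < IMP start date, then not TEAE". A second row covers partial start dates whose known components show "that it cannot be on or after IMP start", and also returns not TEAE. No row or note in the table mentions worsening.

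SAP 11.1 refers to Table 6 for treatment-emergent status "In case of missing or incomplete dates not allowing a direct allocation to any of the two categories of AEs". On reporting, it adds "Pre-treatment AEs will be presented in the listings only".

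**The concern.** The definition and the algorithm give different answers for the same event. An event's class decides whether it reaches a summary table, and TEAE incidence and frequency is the safety endpoint in Protocol 7.1.4 and SAP 3.2.4.

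Events with a pre-dose start will exist. Protocol 8.3 requires adverse events to be documented from consent. Protocol 6.1 puts a wash-out of 8 to 10 days before baseline, during which ophthalmic treatments other than cyclosporine (or equivalent) and preservative-free artificial tears are stopped. Ocular complaints that begin in that interval in patients with severe dry eye, and are then aggravated by a study drop, are events a safety summary ought to show. If such aggravation were more common on one arm, leaving it out would also blunt the comparison between arms.

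**Working it through.** No sample-size, power or alpha figure is involved, so the check is a side-by-side reading of the two rules. Inputs: the definition in SAP 11.1 (same as Protocol 9.4.5), the rows of SAP Table 6, and the recording rules in Protocol 8.2, 8.3 and 8.3.2.

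**Step 1. Compare the rules by recorded start date and worsening.**

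| Recorded AE start | Worsened after first dose? | SAP 11.1 / Protocol 9.4.5 | Table 6 |
|---|---|---|---|
| Known, before IMP start | No | Not TEAE | Not TEAE |
| Known, before IMP start | Yes | TEAE | **Not TEAE: conflict** |
| Partial, must be before IMP start | No | Not TEAE | Not TEAE |
| Partial, must be before IMP start | Yes | TEAE | **Not TEAE: conflict** |
| Known, on or after IMP start | Either | TEAE | TEAE |
| Partial and could be on or after, or missing; stop on or after IMP start, or missing | Yes | TEAE | TEAE |
| As above | No | Depends on the true start | TEAE |

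The conflict is confined to two cells. Where the start is ambiguous or missing, Table 6 leans towards TEAE and keeps worsened events, so those rows need no change.

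**Step 2. Look for text that settles the conflict.** SAP 7.9, which lists changes from the protocol, has no entry on the TEAE definition. SAP 11.1 does not say that it overrides Table 6, and Table 6 does not say that it yields to 11.1.

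**Step 3. Follow a misclassified event.** As a pre-treatment event it goes to the listings. The adverse event tables in SAP 15.1 are of TEAEs and ADRs, so it reaches none of them.

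**Step 4. Check whether the definition can be programmed.** Protocol 8.3 names onset date, outcome, resolution date, intensity, action taken and relationship as the items to document. Protocol 8.3.2 adds "For each episode, the highest severity grade attained should be reported". One record can therefore carry an on-treatment peak grade under a pre-dose onset date, with nothing to show when the grade changed. Unless the eCRF (not among the documents) holds more, the worsening clause in 11.1 cannot be derived from a single record.

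**Step 5. Size.** The documents give no pre-dose event rate, so no count can be computed. A bound per patient can be given. Protocol 4.4 plans about 40 patients per arm and SAP 11.1 counts a patient once per summary. One affected patient therefore lowers the arm's overall TEAE incidence by at most 1/40 = 2.5 percentage points, and by 0 if that patient has any other TEAE.

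**The case against.** The strongest reply is that SAP 11.1 is the definition and calls on Table 6 for TEAE status only when dates do not permit direct allocation. Table 6 also sits in a section on partial dates, and its known-date row has a second use, the split into treatment and follow-up periods. A programmer who reads 11.1 first would keep a worsened event with a complete pre-dose start date. This stands as a limit: the loss is conditional on Table 6 being followed. It does not remove the contradiction. The known-date row states its own TEAE rule, and the partial-date row conflicts with 11.1 even if the table is used for incomplete dates only.

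The second reply is that worsening may be entered as a new event. Protocol 8.2 asks for clinically relevant untoward changes in concomitant conditions, in protocol-specific parameters and in questionnaire responses to be reported as adverse events. A new record with a post-dose onset is a TEAE under Table 6 as written. This also stands in part. But no text tells sites to split an event that worsens, and the single highest grade per episode, together with the Protocol 8.3 preference for one comprehensive event per underlying pathology, points towards one record.

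A reader might go further and infer that every event beginning before the first dose is lost. The documents do not support that: missing or ambiguous starts with a stop date on or after IMP start, or no stop date, default to TEAE. Nor would a misclassified event be counted as unrelated to treatment. Relatedness is the investigator's assessment under Protocol 8.3.1 and is separate from treatment emergence. The event also stays in the listings, and SAE reporting is unaffected.

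**Conclusion.** The contradiction holds, for two rows of Table 6. If those rows are programmed as written, an event that starts between consent and first dose, worsens on treatment and is kept as one record is missing from the TEAE summaries and appears in listings only. This rests on three conditions: Table 6 is followed rather than 11.1, the start is established as before IMP start, and the worsening is not entered as a new event. Exposure is limited to the short interval from consent to first dose. The documents do not allow an estimate of how many events are affected, and any stated percentage loss in TEAE incidence would be an assumption. The correction is worth making because it is cheap, it concerns the safety endpoint, and the choice of rule should not be left open until unblinded data are in hand.

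**What to change.** Reword the two rows of Table 6 (known start before IMP start; partial start that must be before IMP start) so that the event is not TEAE only if there is no worsening in severity after first dose, and is TEAE if there is. Leave the other partial-date and missing-date rows as they are.

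Before database lock, state how worsening is identified: either a date and grade of worsening on the existing record, or a new adverse event record with its own onset date.

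Use that worsening date for the treatment/follow-up assignment as well. That column now works from the start date, so a reclassified event with a known pre-dose start would always fall in the treatment period, even if it worsened during follow-up.

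The cost is an SAP and programming edit. If the eCRF has no field for worsening, a short completion note to sites is needed too. No patient procedures are added.

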#### Figure 1: Study duration

#### 4. General definitions

#### 4.1 Investigational drug and study treatment

Oxervate®, an ophthalmic solution containing cenegermin 20 mcg/mL, which is a recombinant human Nerve Growth Factor (rhNGF); reference product is vehicle. Test and reference will be instilled in both eyes for 28 consecutive days according to the following scheme:

- Group 1: one drop of cenegermin 20 mcg/mL will be instilled in both eyes TID (every 6 hours, e.g. 7:00 am, 01:00 pm; 07:00 pm).
- Group 2: one drop of vehicle will be instilled in both eyes TID (every 6 hours, e.g. 7:00 am, 01:00 pm; 07:00 pm).

Both groups will continue with topical CsA eye drops (or other topical ophthalmic treatment of the same class) as previously prescribed at least 15 minutes apart. The IMP will be provided in a monthly box containing 28 daily vials. Together with the IMP monthly box, patients will be provided with a sufficient number of pipettes and adaptors for the administration of the IMP.

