# 4.4 Visit Schedule and Visit Windows

Assessments and study visits will be performed as listed in Paragraph no. 2 ("Schedule of evaluations") and in Paragraphs no. 6 ("Study Procedure and Assessments") of the Study Protocol [1] containing additional details about scheduled visits and time windows.

Scheduled visits and time windows are:

- Screening (Day -8)
- Visit 1 Baseline (Day 1 + 2 days)
- Visit 2 Week 2 (Day  $14 \pm 2$  days)
- Visit 3 End of treatment Week 4 (Day  $28 \pm 2$  days)
- Visit 4 follow-up Week 8 (Day  $56 \pm 2$  days)
- Visit 5 follow-up Week 12 (Day  $84 \pm 4$  days)
- Visit 6 follow-up Week 16 (Day  $112 \pm 7$  days)
- Visit 7 follow-up Week 24 (Day  $168 \pm 7 \text{ days}$ )

For efficacy and safety endpoints, data will be evaluated according to the Visit at which they have been collected.

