- Summary of Non-Ophthalmic TEAEs by primary SOC and PT and by study period (on treatment/follow-up and overall).
- Summary of TEAEs by primary SOC, PT and Severity.
- Summary of Serious TEAEs by Primary SOC and PT and by study period (on treatment/follow-up and overall).
- Summary of ADRs by Primary SOC and PT and by study period (on treatment/follow-up and overall).
- Summary of ADRs by Primary SOC and PT and Severity.
- Summary of TEAEs leading to IMP Discontinuation by Primary SOC and PT and by study period (on treatment/follow-up and overall).
- Summary of TEAEs leading to study Discontinuation by Primary SOC and PT and by study period (on treatment/follow-up and overall).
- Summary of TEAEs leading to Death by Primary SOC and PT.
- Listing of Deaths.

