| Table 14.3.1.3 Summary of Non-Ophthalmic TEAEs by primary SOC and PT by study periods. Safety set   |     | x              |
| Table 14.3.1.4 Summary of TEAEs by primary SOC and PT by severity. Safety set   |     | x              |
| Table 14.3.1.5 Summary of Serious TEAEs by primary SOC and PT by study periods. Safety set  |     | x              |
| Table 14.3.1.6 Summary of ADRs by primary SOC and PT by study periods. Safety set   |     | x              |
| Table 14.3.1.7 Summary of ADRs by primary SOC and PT by severity. Safety set  |     | x              |
| Table 14.3.1.8 Summary of TEAEs leading to IMP discontinuation by primary SOC and PT by study periods. Safety set   |     | x              |
| Table 14.3.1.9 Summary of TEAEs leading to study discontinuation by primary SOC and PT by study periods. Safety set   |     | x              |
| Table 14.3.1.10 Summary of TEAEs leading to death by primary SOC and PT. Safety set   |     | x              |
| Table 14.3.2.1.1 Compliance to IMP. Full analysis set   |     | x              |
| Table 14.3.2.1.2 Compliance to IMP. Safety set  |     | x              |
| Table 14.3.2.2.1 Extent of exposure. Full analysis set  |     | x              |
| Table 14.3.2.2.2 Extent of exposure. Safety set   |     | x              |
| Table 14.3.2.3.1 Use of preservative free artificial tears. Full analysis set   |     | x              |
| Table 14.3.2.3.2 Use of preservative free artificial tears. Safety set  |     | x              |

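### SAP Table 6 splits treatment completers' TEAEs at a Day 21 visit that does not exist, so the Treatment and Follow-up columns of the by-period safety tables have no valid boundary

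*SAP*

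**What the plan says.** SAP section 11.1 classifies each TEAE as on-treatment or follow-up "according to the available parts of the onset and the end dates (see Table 6"). Table 6, in SAP section 12.5, is therefore the operative rule.

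For an event with a known start date, the relevant row of Table 6 has two branches:

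- **Treatment discontinued:** an event starting after the "Date of last IMP intake, then Follow-up study period for TEAE occurrence". Anything else is Treatment.
- **Treatment not discontinued:** an event starting on or after the "Date of 'Day 21' visit, then Follow-up study period for TEAE occurrence". The fallback is "Otherwise, Treatment study period for TEAE occurrence".

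SAP section 4.1 states that "Test and reference will be instilled in both eyes for 28 consecutive days". SAP section 4.4 labels the Day 28 ± 2 visit "Visit 3 End of treatment Week 4".

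The split feeds several outputs. SAP section 11.1 lists, for example, "Summary of ADRs by Primary SOC and PT and by study period (on treatment/follow-up and overall"), which appears in SAP section 15.1 as "Table 14.3.1.6 Summary of ADRs by primary SOC and PT by study periods. Safety set".

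**The concern.** The completer branch refers to a visit that is in neither schedule and falls a week before planned dosing ends. The rule either cannot be run or has to be reinterpreted by whoever programs it, and the SAP gives no guidance. SAP section 7.9, which lists changes from the protocol, does not mention it.

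The branch matters because it should govern most patients: the protocol plans for about 10% dropout. Protocol section 9.4.5 commits to TEAE analyses by study period. AEs are collected to week 24 (protocol section 8.3), so the split separates 4 weeks on study drug from about 20 weeks after it. Protocol section 2.2 describes an earlier trial in which adverse reactions were confined to the treatment period, so readers are likely to look at these columns. That trial says nothing about onset timing in this one.

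A boundary settled at programming, possibly after unblinding, would also have to be explained as a deviation in the CSR (SAP sections 2 and 7.1).

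**Working it through.** **1. Does any visit cover Day 21?** The schedules in protocol section 2 and SAP section 4.4 agree:

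| Visit | Window (study days) |
|---|---|
| Screening | -8 |
| Visit 1 | 1 to 3 |
| Visit 2 | 12 to 16 |
| Visit 3, end of treatment | 26 to 30 |
| Visit 4 | 54 to 58 |
| Visit 5 | 80 to 88 |
| Visit 6 | 105 to 119 |
| Visit 7 | 161 to 175 |

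None contains Day 21. It lies between Visit 2 and Visit 3, inside the 28 dosing days.

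**2. What does each reading of the rule do?** Take Days 1 to 28 as treatment and Days 29 to 168 as follow-up (168 − 28 = 140 days), for a completer with a known AE start date. The documents give no onset timing, so the results are shares of days.

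- **Study day 21.** Days 21 to 28 move to Follow-up: (28 − 21 + 1)/28 = 8/28 = 28.6%. If Visit 3 and the last dose fall on Day 26: (26 − 21 + 1)/26 = 6/26 = 23.1%.
- **Visit 2 substituted.** Visit on Day 14: (28 − 14 + 1)/28 = 15/28 = 53.6%. Over its window, Day 16 gives 13/28 = 46.4% and Day 12 gives 17/28 = 60.7%.
- **Visit 3 substituted.** Vials are returned at that visit (protocol section 5.5), so assume no dosing after it. At most the visit day moves to Follow-up: 1/28 = 3.6%, or 1/26 = 3.8% if the visit is on Day 26. None moves if the visit falls after the last dose.
- **No such visit, default applied.** No dosing day moves, but all 140 follow-up days are counted as Treatment. They are 140/168 = 83.3% of the study days; with Visit 7 on Day 161, 133/161 = 82.6%, and on Day 175, 147/175 = 84.0%.
- **No such visit, missing date treated as earlier than any date.** This is an assumption about programming. All 28 dosing days would go to Follow-up.

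The error therefore runs from Treatment to Follow-up under some readings and from Follow-up to Treatment under the default.

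**3. Which outputs are touched?** Of the ten TEAE tables 14.3.1.1 to 14.3.1.10, six are split by period: 14.3.1.2, .3, .5, .6, .8 and .9. Table 14.3.1.8 concerns IMP discontinuation and falls under the discontinuer branch, leaving five. In Table 14.3.1.9 only the few patients who completed treatment but left the study because of an AE are affected.

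**4. Does the last-dose rule repair it?** With dosing on Days 1 to 28 and the cut at start date after last dose, 0 of 28 treatment days and 0 of 140 follow-up days are misassigned.

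**The case against.** The strongest reply is that this is a wrong visit label with an obvious repair. If 21 is a slip for 28, the row refers to the end-of-treatment visit and almost nothing is misplaced. A sensible programmer would choose Visit 3. The default reading would leave completers with no known-start event in Follow-up over about 20 weeks, an anomaly that would be noticed. Substituting Visit 2 has no support in the text, since that visit is mid-treatment. The blind data review before lock (SAP section 7.10) offers a chance to correct the label. Finally, the affected columns are descriptive and sit beside an overall column.

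Much of this stands. The Visit 2 figures only illustrate how far an unguided choice could go, and the 83.3% is a share of all study days, not comparable with the shares of dosing days. Taken literally as study day 21, the error runs one way only. The practical consequence is modest.

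It does not remove the point. Nothing in the row shows that 28 was meant, the SAP does not name Visit 3 there, and the blind data review is not committed to resolving it. The choice is left outside the plan.

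**Conclusion.** The concern holds: the completer branch of Table 6 is wrong as written and should be corrected. Depending on the reading, between none and all of the 28 dosing days are counted as Follow-up, or all 140 post-treatment days are counted as Treatment. The literal study-day reading moves 8 of 28 dosing days (28.6%).

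These figures assume dosing on Days 1 to 28 unless stated and describe days at risk, not events. They apply only to patients who did not discontinue treatment and to events with known start dates; partial and missing start dates have their own rows in Table 6.

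The effect is limited to the period columns of Tables 14.3.1.2, .3, .5 and .6, and to a few patients in .9. TEAE status, overall columns, the overview, severity and death tables, the safety endpoint and the efficacy analyses are unaffected. Both arms use the same rule, so no material between-arm bias is claimed.

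**What to change.** Before database lock, replace the Day 21 branch with the rule already used for discontinuers. For every patient with a known AE start date, an event starting after the date of last IMP administration is Follow-up; otherwise it is Treatment. SAP section 4.2 already defines that date and says how to resolve conflicting records. If it is missing, use the End of Treatment visit date.

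The cost is one row of Table 6 and its derivation code, recorded before lock. No data collection changes. The small downside is that an event starting after the last dose but before Visit 3 counts as Follow-up, as it already does for discontinuers. Simply naming Visit 3 in place of Day 21 would be a smaller edit, but keeping the on-or-after comparison could still put the visit day in the wrong period.

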#### Adverse Events:

All AEs (non-serious and serious) that occur during the course of the study will be recorded in the eCRF. Any pre-existing medical conditions or signs/symptoms present in a patient prior to the start of the study (i.e., before informed consent is signed) should be specified in the dedicated eCRF sections. Subsequent to signing an informed consent form, all untoward medical occurrences that occur during the course of the study must be documented on eCRF. AEs will be collected till last Follow Up visit (week 24).

When possible, signs and symptoms indicating a common underlying pathology should be documented as one comprehensive event. For each recorded event, the AE documentation must include the onset date, outcome, resolution date (if event is resolved), intensity (i.e., severity), any action with study treatment taken as a result of the event, and an assessment of the adverse event relationship to the study treatment.

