# **13.2 Listing Conventions**

- Listings will be sorted for presentation in order of subject number, treatment groups (planned), and visit.
- All listings will contain the planned and actual treatment.
- Dates are printed in SAS DATE9.format ("ddMMMyyyy": 01JUL2000). Missing portions of dates are represented on subject listings as dashes (--JUL2000).

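### SAP Table 6 counts a TEAE with a partial start date as on-treatment even when the known month or year puts its onset after the last dose

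*SAP*

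**What the plan says.** SAP 11.1 sets the principle. When dates are missing or incomplete, a TEAE is classed as on treatment or on follow-up "according to the available parts of the onset and the end dates (see Table 6".

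Table 6 in SAP 12.5 is meant to carry this out. Its rows behave differently:

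- **Start date known.** This row has a Follow-up branch. For a patient who discontinued treatment, a start later than the last dose is handled by "Date of last IMP intake, then Follow-up study period for TEAE occurrence". For a patient who did not discontinue, the cut-off is the date of a Day 21 visit.
- **Start date partial and certainly before the first dose.** The row label begins "Partial, but known components show", and the event is not a TEAE. Here the known parts of the date are used.
- **Start date partial otherwise.** The row is labelled "Partial, could be on or after IMP start date". The stop date decides whether the event is a TEAE, and the period rule is then "If TEAE, then Treatment study period for TEAE", without condition.
- **Start date wholly missing.** The period rule is the same.

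Dosing is short relative to observation. SAP 4.1 states "Test and reference will be instilled in both eyes for 28 consecutive days according to the following scheme", while Protocol 8.3 states "AEs will be collected till last Follow Up visit (week 24". Month-only dates are foreseen: SAP 13.2 says "Missing portions of dates are represented on subject listings as dashes (--JUL2000".

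**The concern.** A partial start date can be uninformative about the period, or it can settle it. If the known month lies wholly after the last dose, onset on treatment is impossible, yet Table 6 still returns Treatment. The table checks known components against the first dose but makes no matching check against the last dose, although SAP 11.1 calls for one.

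The consequence falls on the tables split by study period that SAP 11.1 and Protocol 9.4.5 prespecify. Events moved in this way inflate the on-treatment columns and empty the follow-up columns. The split matters for this product: Protocol 2.2 reports that in the earlier phase II study adverse reactions were confined to the four weeks of dosing. Under Table 6, a follow-up reaction dated only to the month cannot appear as a follow-up reaction, so the rule could by itself help to reproduce that pattern.

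**Working it through.** The plan gives no figure on this point to reproduce. The check is a trace of the rule, followed by a count of calendar days.

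**Inputs.** Dosing lasts 28 days (SAP 4.1). AEs are collected to week 24, nominally day 168 (Protocol 8.3 and visit schedule). Follow-up onset days are therefore 168 − 28 = 140. Assumptions: only the day of onset is missing, the full 28 days are dosed, last contact is on day 168, and all onset days have equal weight.

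**Step 1: one event traced.** Take a first dose on 5 September 2022. Day 28 is 2 October 2022 and day 168 is 19 February 2023. An AE start is recorded as January 2023 with the day unknown.

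- The earliest compatible onset is 1 January 2023. That is 29 + 30 + 31 + 1 = 91 days after the last dose.
- The date is partial and could be on or after the first dose, so the partial-start row applies. With a stop date on or after the first dose, or no stop date, the event is a TEAE.
- Table 6 returns Treatment.
- The same event dated 15 January 2023 would be Follow-up under the known-date row.

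**Step 2: share of follow-up days that month and year would place correctly.** Let r be the number of days left in the calendar month after the last dose. Those r days are ambiguous, and every later follow-up day is provably after dosing. The share is (140 − r)/140.

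- Last dose on the first of a 31-day month: r = 30, share = 110/140 = 79%.
- Last dose on the last day of a month: r = 0, share = 100%.
- Average over 365 start dates: a month of m days contributes m(m − 1)/2 to the sum of r. The total is 7 × 465 + 4 × 435 + 378 = 5,373, so mean r = 5,373/365 = 14.7. The mean share is 1 − 14.7/140 = 0.895. Direct enumeration of the 365 start dates gives 0.8949, with range 0.786 to 1.

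Table 6 places 0% of these days in Follow-up.

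**Step 3: share of month-dated TEAEs provably misassigned.** This is about 0.89 × f, where f is the fraction of such onsets that fall in follow-up. The documents do not give f, so a range is needed:

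| f | Provably misassigned |
|---|---|
| 140/168 = 83% (uniform onset) | about 75% |
| 50% | about 45% |
| 20% | about 18% |
| 0% | 0% |

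**Step 4: outputs touched.** These are the by-period tables of ophthalmic TEAEs, non-ophthalmic TEAEs, serious TEAEs, ADRs and TEAEs leading to study discontinuation. An event that caused the study drug to be stopped should not begin after the last dose, so that table is essentially unaffected. Overall TEAE counts, severity tables and efficacy do not use the period assignment.

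**The case against.** The best defence is that assigning uncertain onsets to treatment is a common cautious convention, because it does not understate on-treatment risk. That stands for wholly missing start dates and for partial dates that overlap dosing. It does not cover a date whose known parts already exclude dosing, since nothing about the period is then uncertain.

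The second defence is that few events, perhaps none, will be affected. About 80 patients are planned. Protocol 8.3 requires an onset date for every AE, diaries run through follow-up, and edit checks and queries pursue incomplete entries (Protocol 11.2). If reactions again cluster within the dosing weeks, the misassigned share of the ADR table is near zero. Partial dates also remain visible in Listing 16.2.7.1. All of this limits the practical effect, and none of it makes the rule correct.

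Third, Table 6 is broken in the text available for review. The period cell in the partial-start row stops early, and the cells below it are blank. They are most naturally one merged cell covering all stop-date cases. On the narrowest reading, partial start with known stop date, the rule is still unconditional. Further lost text is unlikely but cannot be excluded.

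**Conclusion.** The point holds in a limited form. For partial start dates whose known month or year excludes the treatment period, Table 6 gives a provably wrong period and contradicts SAP 11.1; no override was found elsewhere in either document. Under the stated assumptions, month and year would recover about 89% of follow-up onset days (79% to 100%), against none under the rule. The share of month-dated TEAEs affected runs from 0% to about 75%, depending on when onsets occur. The number of partial-date AEs is not given, so no count of misplaced events can be stated. This is a minor, easily corrected defect.

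A reader might infer more than the documents support:

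- That three-quarters of all TEAEs will be misplaced. The 75% requires uniform onset and applies only to events with month-only dates.
- That the treatment of wholly missing dates is also wrong. Those dates carry no month to contradict the default.
- That every discontinuation table is distorted. Of the two, only the study-discontinuation table can be materially affected.
- That overall safety totals are inflated. Events move between columns, and their number does not change.

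**What to change.** In the partial-start row of Table 6, assign Follow-up if the earliest date compatible with the known components is after the end-of-treatment boundary, and Treatment otherwise. Keep Treatment for wholly missing start dates.

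The boundary has to be settled at the same time. For known dates, Table 6 uses the last IMP intake after discontinuation but a Day 21 visit for everyone else, and the schedule in SAP 4.4 has visits at days 14 and 28 and none at day 21. If only the partial row were changed, completers could have partial and complete dates split at different points. Use one boundary throughout, for example the date of last administration as defined in SAP 4.2, in place of the Day 21 cut-off.

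The cost is small: one added condition in the partial-start row, one replaced cut-off in the known-date row, and the matching lines of the derivation program. No new data are needed. The change should be made before unblinding.
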